One in six men will develop prostate cancer [20]. Due to the widespread use of PSA testing, cancer is often detected before systemic disease occurs [2]. Depending on clinical presentation, therapy is typically approached through locally directed interventions such as radical prostatectomy, brachytherapy, external beam radiotherapy or cryotherapy. Yet, approximately, 30% of patients treated with definitive local therapy experience recurrent disease [2, 3].

Recurrent disease usually manifests with rising PSA. The differentiation of local from extraprostatic recurrence is of critical importance since salvage techniques can cure disease confined to the prostate bed. If pelvic nodal involvement is suspected, radiation fields can be extended to include the pelvic nodes [4-6]. Systemic disease is treated with hormonal manipulation and/or chemotherapy. PSA level is not useful in the differentiation of local from extraprostatic recurrence, though the rate of PSA rise may have some value [21].

Imaging plays a central role in the detection of recurrent prostate carcinoma in the prostate bed and in the differentiation of prostatic from extraprostatic recurrence. Conventional methodology including computed tomography (CT), magnetic resonance imaging (MR), transrectal ultrasound, bone scan and ¹¹¹Indium-capromab-pendetide (ProstaScint) (EUSA Pharma, Langhorne, PA) may provide important information, but suffer from less than optimal diagnostic performance [22-30]. Newer methods such as diffusion weighted MR (DWMR) and positron emission tomography (PET) with molecular radiotracers are currently under study for the characterization of post-therapy recurrence [11-19]. MR with superparamagnetic (USPIO) particles has shown promise but is not available in the US [19]. The sensitivity of most imaging techniques is dependent upon PSA level, doubling time, and velocity [16, 31, 32].

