As has been outlined in the Preliminary Results section of this proposal, *anti*-[¹⁸F]FACBC has been demonstrated to 1) have high sensitivity in the detection of recurrent prostate carcinoma though with suboptimal specificity in the prostate bed, and 2) the ability to differentiate prostatic from extraprostatic recurrence with high accuracy. *anti*-[¹⁸F]FACBC may thus have specific advantages for imaging recurrent prostate neoplasia within a clinical setting over conventional imaging. Yet, MR, especially with the addition of diffusion weighted imaging, has been reported in preliminary studies to provide high accuracy especially in the characterization of prostate bed recurrence. We hypothesize that utilization of a transmolecular approach combining synthetic amino acid radiotracer PET imaging with multiparametric MR has the potential to identify the presence and location of recurrent prostate carcinoma to a higher accuracy than either modality alone. **Therefore the most comprehensive manner to assess our hypothesis that PET-CT imaging with *anti*-[¹⁸F]FACBC in combination with multiparametric MR will lead to improved patient care resulting from detection of local and distant recurrent disease (Specific Aim #1) is to undertake a prospective clinical trial designed to address these issues.**

Secondary Aims

Aim 2. To determine mRNA differences between prostate carcinoma recurrent in the prostate bed and extraprostatic locations and to correlate any difference with quantifiable imaging biomarker data such as SUV for *anti*-[¹⁸F]FACBC PET-CT and ADC for MR.

Within the structure of the clinical trial (the same 25 patients) we will obtain sufficient tissue to perform mRNA sequencing on samples to exploit differences between the genetic profiles of recurrent prostate carcinoma in the prostate bed versus metastases. Since approximately 30% of patients with PSA > 4 ng/ml by our experience manifest with both prostate bed and nodal recurrence, we believe at least 8-10 patients in whom this comparison can be directly made will be available for analysis. This may also occur with lower PSA levels with faster DT. We will then correlate any differences in genotypic profile with imaging biomarkers from synthetic amino acid PET and MR, such as SUV and ADC.

Sub-aim 2a. To evaluate protein expression of previously identified amino acid transporters (AATs) that have been implicated in the uptake of *anti*-[¹⁸F]FACBC.

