Also within the context of the clinical trial of 25 patients, we will, whenever there is sufficient tissue, determine if candidate amino acid transport (AAT) proteins identified from data obtained in an earlier study (Project 1: P-50 ICMIC) are expressed. We will perform IHC analysis of up to 7 candidate AAT or co-transporters, specifically PAT 1, LAT1, LAT2, 4F2hc, and ASCT2, LAT3 and ASCT1 to understand if the AAT whose mRNAs are increased in malignant prostate carcinoma and correlated with *anti*-[¹⁸F]FACBC uptake are expressed at the protein level by IHC analysis.

Rationale for Aim 2 and Sub-aim 2a.

As has been outlined in the Preliminary Results section of this proposal, there is preliminary data in the literature of gene expression and mutational differences between primary prostate carcinoma cells and those prostate metastases [7-9] as well as between bone metastases and non-osseous metastases [8]. We propose within the context of this clinical trial to provide tissue to further understand these differences both in the ability of prostate carcinoma to transport and retain amino acids measured as uptake of *anti*-[¹⁸F]FACBC and expression characteristic as studied by multiparametric MR such as ADC parameters on DWMR and uptake and retention of Gadolinium. If we can determine that there are gene expression differences between malignancy confined to the prostate bed and those that are extraprostatic, we can correlate these differences to PET uptake and MR appearance. Furthermore, we may also be able to derive incidental genotypic information that could be exploited on subsequent unrelated experiments. In addition, we have preliminary evidence based on our earlier research that PAT1, LAT2 and ASCT2 as well as LAT1, xCT, LAT3 and ASCT1 were associated with malignancy. Out of the AATs that were associated with malignancy, PAT1 expression had the strongest correlation coefficient relative to *anti*-3-[¹⁸F]FACBC uptake [38]. We believe that a study such as this one provides an ideal opportunity to obtain both prostatic and extraprostatic tissue from the same patient in order to test these hypotheses using the patient as his own control.

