Upon completion of the study and/or after additional follow-up, each patient may be re-reviewed by the same Ground Truth Panel to determine if the predicted findings on *anti*-[¹⁸F]FACBC scan and MR individually and in tandem match those of clinical and pathologic findings especially in regard to the identification of prostatic versus extraprostatic recurrence. Also at that time uptake parameters will be reviewed. At no time this study will interfere with proper therapy as determined by the patient's physicians and the patient.

C2.0 Study Design and Methods (Aim2 and Sub Aim 2a)

Rationale. We hypothesize that *anti*-[¹⁸F]FACBC uptake is mediated by a LAT protein subtype or subtypes. However, the precise LAT subtype involved in all cases is unknown. We also further hypothesize that there are genotypic differences between recurrent prostate carcinoma cells confined to the prostate bed and those that are extraprostatic and that these differences can be explored via proper identification of candidate tissue via transmolecular imaging to be performed at termination of study or when sufficient tissue has been collected.

Experimental Design. To test the above hypothesis, we will compare mRNA expression of recurrent prostate carcinoma tissue within the prostate bed and extraprostatic. In addition we will utilize *anti*-[¹⁸F]FACBC avid tissue to confirm that the following AAT subtypes based on preliminary data are expressed at the protein level: PAT 1, LAT1, LAT2, 4F2hc, and ASCT2, LAT3 and ASCT1. We will study 8-10 samples of each recurrent prostate carcinoma in the prostate bed and 8-10 samples of disease outside the prostate bed, preferably in the same patient. We predict that one or more AAT subtypes will be relatively overexpressed by IHC in FACBC-avid carcinoma. We also predict that there will be differences in mRNA expression

based on these tissue samples between disease confined to the prostate bed and those that are extraprostatic. Based upon tissue availability we will perform IHC in the following rank priority: First: PAT 1; Second: LAT1, LAT2, 4F2hc; Third: ASCT2, LAT3 and ASCT1. This priority ranking is based on our desire to first confirm phenotypic expression of PAT1, since presence of this AAT correlated most strongly with *anti*-[¹⁸F]FACBC uptake, followed by LAT1 and LAT2 with the heterodimeric associated protein 4F2hc, and ASCT2, LAT3 and ASCT1.

C 2.1 Quantitative next-generation mRNA sequencing

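### Aim 2 is hypothesised as disease confined to the prostate bed versus extraprostatic disease, but same-man sampling mostly measures a lesion-site difference and supports no conclusion about confined disease

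*Combined protocol and SAP*

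**What the plan says.** The plan words the Aim 2 contrast in two ways.

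**As confined versus extraprostatic disease.** The C2.0 rationale hypothesises "genotypic differences between recurrent prostate carcinoma cells confined to the prostate bed and those that are extraprostatic", and the Experimental Design paragraph predicts expression differences "based on these tissue samples between disease confined to the prostate bed and those that are extraprostatic". The Rationale for Aim 2 and Sub-aim 2a refers to "gene expression differences between malignancy confined to the prostate bed and those that are extraprostatic". The second hypothesis in the opening section uses the same term.

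**As tissue site.** Aim 2 in the Secondary Aims reads "To determine mRNA differences between prostate carcinoma recurrent in the prostate bed and extraprostatic locations". The sentence that opens the C2.0 Experimental Design and the analysis text in E2.0 also compare samples by site.

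The sampling follows the second wording. C2.0 plans 8-10 bed samples and "8-10 samples of disease outside the prostate bed, preferably in the same patient". The Rationale says that the trial is an opportunity to "obtain both prostatic and extraprostatic tissue from the same patient in order to test these hypotheses using the patient as his own control". Under Aim 2 the plan states that "we believe at least 8-10 patients in whom this comparison can be directly made will be available for analysis".

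Neither C2.0 nor E2.0 labels a bed sample by whether the man also has extraprostatic disease. Bed samples from bed-only men are neither required nor excluded.

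**The concern.** Elsewhere the protocol uses *confined* to describe the patient. Background and Significance says that "salvage techniques can cure disease confined to the prostate bed", and sets this against men who need nodal fields or systemic treatment. In that sense, a man who supplies both a bed and a nodal sample has no confined disease, so his bed sample cannot represent it. The more fully the same-man preference is met, the fewer confined cases the bed group contains.

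Pairing within a man asks whether expression differs between two lesions of the same cancer. Whether a cancer that stays in the bed differs from one that has spread is another question, and it needs bed tumour from men of both kinds.

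What is at stake is how the result is read. Against the prediction as written, a null result could be taken to mean that confined and extraprostatic disease do not differ, and a positive result could be taken as a feature of confined disease. Neither reading follows from these samples. If some bed-only men are added without a label, the bed group becomes an undocumented mixture.

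**Working it through.** **Inputs**
- Prior PSA ≥ 4 counts, n = 73 (Rationale for Aim 2 table): bed only 41, both sites 25, nodes only 1.
- Rate of both sites stated in the Aim 2 text: about 30%.
- Trial size: 25 men. Planned samples per site (C2.0): 8-10.

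**Step 1. Reproduce the plan's expected yield**
- Any bed disease: 25 × (41 + 25)/73 = 22.6 (plan: about 23).
- Any nodal disease: 25 × (25 + 1)/73 = 8.9 (plan: about 9).

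Both figures reproduce.

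**Step 2. Split that yield**
- Both sites: 25 × 25/73 = 8.6 men (at the stated 30%: 25 × 0.30 = 7.5).
- Bed only: 25 × 41/73 = 14.0 men.
- Nodes only: 25 × 1/73 = 0.3 men.

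The expected number of same-man pairs is thus close to the number of bed samples planned. The 14 or so men with confined disease would be used mainly to fill a shortfall.

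**Step 3. How many bed samples would be confined disease?**

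Assume that pairs are used first and that bed-only men fill any shortfall up to a target T. Let X, the number of men with both sites, be Binomial(25, p).
- Chance of no confined case = P(X ≥ T).
- Expected confined cases = Σ max(0, T − x) · P(X = x).
- Share of bed samples that are not confined = 1 − expected confined cases / T.

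| p | T | Chance of no confined case | Expected confined cases | Share not confined |
|---|---|---|---|---|
| 25/73 | 8 | 67% | 0.7 | 92% |
| 25/73 | 9 | 50% | 1.2 | 87% |
| 25/73 | 10 | 34% | 1.8 | 82% |
| 0.30 | 8 | 49% | 1.2 | 85% |
| 0.30 | 9 | 32% | 1.9 | 79% |
| 0.30 | 10 | 19% | 2.7 | 73% |

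**Step 4. What the sampling is suited to**

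Take a site difference of 1 SD, two-sided alpha 0.05, and assume that the SD of the within-man differences is also 1. The power of a paired t-test is 68%, 75% and 80% at 8, 9 and 10 pairs. Two independent groups of 8, 9 or 10, with an SD of 1 in each, give 46%, 51% and 56%. Pairing is therefore a reasonable choice for a site contrast, provided that the analysis is also paired. E2.0 does not say that it is, and its rank sum alternative is an unpaired test.

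**The case against.** The strongest reply is that this is a matter of wording. Aim 2 is stated by site, as are the sentence describing the comparison in C2.0 and the analysis in E2.0. The C2.0 hypothesis speaks of cells, so *confined* can be read as describing where the cells lie. The own-control sentence shows that a within-man contrast was intended. The stated use of the results is correlation with SUV and ADC, which are measured on lesions. Much of this stands: Aim 2 as worded is not invalidated, and pairing suits it. What does not go away is that the hypothesis and prediction use a term that Background and Significance applies to patients, and nothing tells the reader that the narrower meaning applies.

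A reader might infer that the bed group *cannot* contain confined cases. The plan does not support that. Same-man sampling is a preference, and about 14 bed-only men are expected. Pairs may also be fewer than in the table. In the PSA < 4 column only 8 of 54 men had both sites, which for 25 such men would be 25 × 8/54 = 3.7. The trial admits men with PSA 2.0-3.99, although only with a short doubling time, for which the protocol expects more extraprostatic disease. Biopsy depends on clinical judgement, and RNA must pass quality limits.

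A reader might also want to show by simulation that the planned comparison is blind to a confined-versus-spreading difference. If a 1 SD effect is placed wholly at the level of the man and shared by his lesions, a paired test rejects about 5% of the time, against about 61% for bed tumour in 9 men with spread versus 14 bed-only men. This should not be used as evidence. Under that assumption the effect cancels within each pair, so the 5% is simply alpha. It also leaves out any difference between lesion sites, which is what Aim 2 looks for.

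**Conclusion.** The point holds as a mismatch between what Aim 2 hypothesises and what its samples can show. With pairs used first, about 73-92% of bed samples would come from men whose disease is not confined. The expected number of confined cases is 0.7 to 2.7 among 8-10 bed samples, and the chance of none is 19-67%. The comparison estimates a lesion-site difference and supports no conclusion about confined versus spreading disease.

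These figures assume that the PSA ≥ 4 proportions (or the stated 30%) apply to all 25 men, that every positive site yields usable tissue, and that pairs take priority. More men with low PSA or more tissue failures would probably raise the number of bed-only samples. That would make the bed group more of a mixture without making it a confined group.

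The documents do not support the wider readings that Aim 2 is unsound, or that confined cases are certain to be absent.

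**What to change.** 1. Restate the hypothesis, the prediction and the planned conclusion as a site contrast, bed lesion versus extraprostatic lesion, wherever *confined* is now used (opening section, Rationale for Aim 2, C2.0), so that they agree with Aim 2.
2. Label each bed sample by the man's extraprostatic status as determined by the Ground Truth Panel (C1.7), with an undetermined category, since C1.7 allows that some men will lack definitive extraprostatic follow-up.
3. Report bed samples from bed-only men separately from the same-man pairs.
4. Optionally, where tissue has already been assayed, report bed tumour in bed-only men against bed tumour in men with extraprostatic disease, marked as exploratory. This is a new question with modest power: about 61% for 1 SD at 14 versus 9 men, for a single gene without multiplicity correction and with usable tissue from every man. Extending it to further samples would draw on limited tissue and add assay cost.

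Items 1 to 3 need only changes of wording and one extra data field. Their downside is a narrower stated conclusion.

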3) For *anti*-3-¹⁸F]FACBC, uptake will be defined according to the following criteria in relation to background structures: mild (above blood pool but less than marrow), moderate (above or equal to marrow but less than liver), and intense (equal to or above liver). Visual analysis will be aided by quantitative criteria of SUV_{max} lesion/SUV_{mean} background. Maximum and mean SUV of each focus of abnormal uptake as well as background structures including liver, marrow at L3, aorta, and bladder will be recorded. For prostate beds as well as extra-prostatic sites such as lymph nodes and bone, abnormal moderate or intense focal uptake over background marrow which persist from early to delayed images will be considered prospectively positive. These criteria were used to analyze data in our study of *anti*-¹⁸F]FACBC in recurrent disease [40].

4) Confidence in interpretation for disease within the prostate bed and outside the bed will be recorded with the following scale on a per patient basis and any all recordable lymph nodes: 1- definitively negative; 2 -probably negative; 3 - indeterminate; 4 - probably positive; 5 – definitively positive.

5) In summary, we will record both visual and semi-quantitative analysis of the prostate bed, positive lymph nodes (greater than blood pool), and other structures such as skeletal foci on early and delayed time frames. We will use maximum and mean SUV as well as standard bidimensional size measurements. We will also record similar measurements on background structures such that we may derive uptake ratios.

C1.5 Image Analysis of MR

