The MR studies will be interpreted by an MR imager. (At some point after primary analysis, a 2nd interpretation may also be blindly performed and agreement (Z Value) recorded.) Studies will be interpreted utilizing standard interpretative criteria for MR and including anatomic criteria, perfusion analysis and DWMR criteria. Confidence in interpretation for disease within the prostate bed and outside the bed will be recorded for each of these three interpretative categories individually and in aggregate with the following scale on a per patient basis and any all recordable lymph nodes: 1-defiinitvely negative; 2 -probably negative; 3 - indeterminate; 4 - probably positive; 5 – definitively positive. Typically, a combination of abnormality on all relevant sequences will result in a “5” (e.g. DCE, DWI, and T2), while no abnormality on any sequence will result in a “1”. A combination of suspicious and benign findings on pulse sequences will result in a “2”, “3”, or “4” depending on particular findings.

C1.6 Image Analysis of PET-MR

After individual interpretation of each study, then the PET and appropriate sequences from the MR (typically post-contrast abdominopelvic supplemented by other sequences) will be co-registered using rigid software registration on a MimVista 5.5 or similar workstation. The studies will then be analyzed by consensus by one of the 2 nuclear imagers and the primary research MR imager. All foci previously recorded by each group as positive or negative will then be assessed by the group taking into account all parameters previously employed. New foci may also be identified. Confidence in interpretation for disease within the prostate bed and outside the bed will then be recorded with the following scale on a per patient basis and any all recordable lymph nodes: 1-defiinitvely negative; 2 -probably negative; 3 - indeterminate; 4 - probably positive; 5 – definitively positive. Typically agreement on both studies will be recorded

as “1” or “5”, and combination of lack of agreement in a “2”, “3”, or “4” depending on particular findings.

C1.7 Clinical and Histologic Assessment.

Methods. After the *anti*-[¹⁸F]FACBC scan has been obtained and interpreted, the following will occur:

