Receiver Operating Characteristic (ROC) analysis will be conducted to instigate the predictive power of FACBC PET and MR and determine if a variation in standard criteria or if combined criteria better maximizes sensitivity, specificity and accuracy of *each technique* using Chi-square test. The predictive accuracy of each technique will be determined using the positive predictive value (PPV) relative to the clinical and pathologic findings. The PPV of imaging will be assessed by calculating the probability of obtaining clinical and pathological outcomes that confirm the predicted positive findings based on the individual and combined scans. A similar negative predictive value (NPV) will also be calculated based upon a negative pathologic sampling as well as clinical/imaging follow-up at least 1 year or more. Formal hypothesis testing will be conducted to obtain inferences regarding differences between the predictive accuracies of these two approaches.

Each case will be evaluated as follows:

- 1) Results of biopsy as well as clinical follow-up will be correlated with prediction of local and distant neoplastic involvement by MR and *anti*-[¹⁸F]FACBC PET-CT.
- 2) Results of biopsy of lymph nodes or other extra-prostatic sites as well as clinical follow-up will be correlated with prediction of extraprostatic neoplasia by MR and *anti*-[¹⁸F]FACBC PET-CT.
- 3) Registered PET and MR will be correlated both qualitatively and quantitatively to pathologic and clinical results and in the discrimination of prostatic from extra-prostatic recurrence.
- 4) **Thus, truth for presence of disease will be established by biopsy/pathology and/or appropriate clinical followup. Truth for absence of disease will be established via pathologic sampling as well as standard clinical follow-up for at least 6 months and up to five years. We believe there will be enough patients with biopsy and clinically followed-up negative lymph nodes to calculate a true negativity rate.**

E2.0 Secondary Aims

Aim 2. and Sub-aim 2a.

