Depending on the normality of data distribution, t-test or Wilcoxon rank sum test will be conducted to compare the mRNA differences, genomic differences in gene expression, alternative splicing, indels and single base mutations between prostate carcinoma recurrent in the prostate bed and extraprostatic samples. Analysis of variance (ANOVA) will be used to compare the IHC staining of protein levels between the different categories of FACBC uptake. Tukey pairwise comparison will be further conducted when the overall comparison with ANOVA

Version 9-23-13

Version 11-6-13

Version 11-11-14

Version 12-4-14

is significant at the significance level of 0.05. Pearson/Spearman correlation coefficients will be estimated to measure the associations: 1) between mRNA levels of candidate AAT genes and FACBC uptake; 2) between mRNA differences and quantifiable imaging biomarker data such as SUV for *anti*-[¹⁸F]FACBC PET-CT and ADC for MR. Multivariate analyses will further be conducted, in which general linear model (GLM) will be employed to assess the adjusted relationships mentioned above after adjusting for the other covariates.

Sample size and power calculation

The sample size of this study is 25 patients. The power calculation is based on the comparison of mRNA differences between the prostate bed and extraprostatic samples using two sided t-test. At the significance level of 0.05, the sample size of 25 will achieve a power of at least 80% to detect one standard deviation or higher difference in mRNA difference between the two groups of samples.

F. Adverse Event Reporting

An adverse event is defined as any untoward medical occurrence associated with the use of a drug in humans whether or not considered drug-related

A significant shift from baseline which can be attributable to the radiotracer injection and not the patient's medical condition will be considered an unexpected AE. An event greater than 7 days post scan will not be considered an AE since 95% of ligand is eliminated by 7days.

The National Cancer Institute's Common Terminology Criteria for Adverse Events (CTCAE) Version 4.03 (June 14, 2010) will be used as a guide address potential AEs subject to limitations above and medical and scientific judgment as to plausibility of such criteria in a diagnostic radiotracer study.

Adverse Event Reporting

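### Aim 1 would choose diagnostic cut-offs and score them on the same 25 men, with no correction for optimism and no stated cut-off for MR or fused PET-MR

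*Combined protocol and SAP*

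**What the plan says.** Section E.1 (Aim 1) begins with ROC analysis of FACBC PET and MR, to "determine if a variation in standard criteria or if combined criteria better maximizes sensitivity, specificity and accuracy" of each technique. It then defines PPV and NPV for the individual and combined scans and adds: "Formal hypothesis testing will be conducted to obtain inferences regarding differences between the predictive accuracies of these two approaches".

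The data are one cohort. The sample size paragraph states "The sample size of this study is 25 patients", and no other data set is named for Aim 1.

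The positivity rules differ by technique:

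- **PET (C1.4).** A visual rule is fixed in advance: "abnormal moderate or intense focal uptake over background marrow which persist from early to delayed images will be considered prospectively positive". A 1-5 confidence score is recorded as well, with no cut-off and no stated link to the visual rule.
- **MR (C1.5).** "Studies will be interpreted utilizing standard interpretative criteria for MR and including anatomic criteria, perfusion analysis and DWMR criteria". Confidence is scored 1-5 for each of those three categories and in aggregate. No cut-off is stated.
- **Fused PET-MR (C1.6).** "All foci previously recorded by each group as positive or negative will then be assessed by the group", and a consensus 1-5 score is given. No cut-off is stated.

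Neither the imaging sections nor E.1 lists the candidate criteria, names one metric to maximise, or provides for a training and test split, cross-validation, bootstrap correction or a validation cohort.

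**The concern.** A cut-off picked because it performs best in a sample has partly fitted that sample's noise. Scored on the same men, it looks better than it would in new patients. If the standard rule is among the candidates, the winner cannot lose to it on the metric used for the choice. A test of the winner against the standard is then not a fair test.

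The preset PET rule does not remove the problem, because E.1 sets out to examine variations of it. For MR and the fused read, PPV and NPV cannot be calculated until someone decides which scores count as positive. Blinded scoring protects the scores. It does not protect the choice of cut-off, which the plan allows to be made after truth is known.

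At stake are the accuracy figures and tests for any optimised criterion, and the planning of the more comprehensive study that the Background says these data could help design.

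**Working it through.** **Plan's own figures.** Aim 1 has no power, precision or sample-size figure to reproduce. The expected disease counts, in the rationale for Aim 2 and Sub-aim 2a, do reproduce from the table for PSA of at least 4:

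- Bed: 25 × (41 + 25)/73 = 22.6, about 23 with disease and 2 without.
- Nodes: 25 × (1 + 25)/73 = 8.9, about 9 with disease and 16 without.

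**Why the direction is certain.** Let S be the set of candidate rules and m(r) the chosen metric for rule r in the sample. The winner scores max m(r) over S. If the standard rule r0 is in S, then max m(r) ≥ m(r0) in every sample, whatever the truth.

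**Size at the nodes (9 and 16).** Assumptions, not from the documents: scores are normal with SD 1, and the means of men with and without disease are d' apart. In each of 10,000 simulated trials, the cut-off c that maximises (sensitivity + specificity)/2 is chosen. The apparent value is that maximum. The true value is [Φ(d' − c) + Φ(c)]/2. The five-point scale uses cut-offs at −0.5, 0.25, 0.75 and 1.5 SD above the mean of men without disease. Evenly spaced cut-offs around d'/2 change the results by at most 0.01.

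The range of d' is 1 to 2.1. The upper end is near the nodal DWMR figures in the Background (sensitivity 86%, specificity 85.3%): 1.08 + 1.05 = 2.13.

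| d' | Five-point: apparent vs true | Continuous: apparent vs true | Best fixed continuous cut-off, Φ(d'/2) |
|---|---|---|---|
| 1.0 | 0.73 vs 0.67 | 0.77 vs 0.67 | 0.69 |
| 1.5 | 0.80 vs 0.75 | 0.84 vs 0.75 | 0.77 |
| 2.1 | 0.87 vs 0.83 | 0.90 vs 0.83 | 0.85 |

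The optimism is 4 to 6 points on the five-point scale and 7 to 10 points for a continuous cut-off. If the standard were the best fixed continuous cut-off, the chosen one would look 5 to 8 points better and truly be about 2 points worse.

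**Several criteria sets.** Taking the best of three independent five-point sets gives 9 to 12 points. For three sets this is an upper bound, because scores on the same man are correlated.

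**Bed (23 and 2).** The same method gives 11 to 18 points; for example, 0.83 vs 0.65 for a continuous cut-off at d' = 1. Specificity can only be 0, 0.5 or 1, so this figure is very uncertain. It also depends on the metric. Calling every man positive already gives 23/25 = 92% plain accuracy, and optimism in plain accuracy is small there (0.00 to 0.05 in the second simulation).

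**Second simulation, for the limits of the argument.** It used two independent five-point scores (PET and MR), with PET score ≥ 4 as the standard and a separation of 0 or 1.2 SD. The candidates were 4 PET cut-offs or 40 single and AND/OR rules. There were 16 settings of 3,000 trials.

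- The chosen rule matched or beat the standard on the maximised metric in 100% of trials in every setting, and beat it strictly in 56% to 100%.
- Sensitivity and specificity were both at least as high as the standard's in only 22% to 82% of trials.
- A combined read scored at a cut-off fixed in advance, with the same true accuracy as PET, matched or beat PET on accuracy in only about 56% to 57% of trials. The guarantee does not extend to it.
- A real gain is still overstated. For nodes at 1.2 SD, with PET cut-offs chosen on accuracy, the apparent gain was 0.761 − 0.697 = 0.064 and the true gain 0.725 − 0.698 = 0.027.

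**The case against.** The trial is called preliminary, and exploring cut-offs is ordinary at that stage. The PET rule is fixed prospectively and comes from an earlier study. The fused read is expert consensus, not a fitted formula. The MR and fused scales carry verbal labels under which 4 and 5 naturally read as positive, so only score 3 is really open. The assumed separation comes from no document, and at the upper end of the range the optimism on a five-point scale is only 4 points.

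Most of this is fair, and it limits the size of the point. It does not remove it: formal tests are planned, nothing is labelled exploratory, and a label that suggests a cut-off does not commit anyone to it.

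A reader might also infer four stronger things that the documents do not support:

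- **That the bias favours PET-MR over the single techniques.** MR has four scores per site and the fused read has one, and E.1 speaks of criteria for each technique. Optimising every technique inflates all of them. No net direction is shown.
- **That Aim 1's PPV and NPV are necessarily inflated.** E.1 does not say that they use the optimised cut-offs.
- **That sensitivity, specificity and accuracy must all look better.** The guarantee covers only the metric maximised, and only when the standard rule is a candidate.
- **That the plan states it will reuse the same men.** This is inferred, because no other data set is named.

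**Conclusion.** The point holds in a limited form. The plan searches for a better criterion, follows the search with formal tests, names only one cohort of 25, and neither corrects for the search nor labels it exploratory. The direction of the bias follows from the procedure. Its size does not: about 4 to 10 points of balanced accuracy at the nodes for a single search, with up to 9 to 12 points for the best of three five-point criteria sets, and larger but very uncertain in the bed.

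These figures rest on normal scores, an assumed d' of 1 to 2.1, and approximate disease splits. The splits come from men with PSA of at least 4, and the documents do not say whether those counts are confirmed disease. C1.7 allows fewer evaluable men in each sub-analysis, which would tend to increase the optimism. The absence of a stated cut-off for MR and fused PET-MR needs no assumption; it can be read directly from C1.5 and C1.6.

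**What to change.** Before the Ground Truth Panel meets, write one positivity rule per technique into the SAP: the C1.4 visual rule for PET, and a score of 4 or higher for MR and for fused PET-MR. Score 3 then counts as negative. State which MR score is used; the aggregate score is the natural choice.

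Base sensitivity, specificity, PPV, NPV and every formal test on these rules. Label any ROC-optimised or combined criterion exploratory. Name the single metric it maximises and list the candidates searched. Report it with bootstrap optimism correction, or with leave-one-patient-out cross-validation, repeating the whole search in each resample. For the bed, say plainly that about two negatives cannot support an optimised cut-off.

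The cost is a paragraph of SAP text and a short resampling program. No extra patients, scans or biopsies are needed. The downside is that the reported accuracy of optimised criteria will be lower.
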